9 ADVERSE EVENTS

9.1 Definitions

9.1.1 Adverse Event

An Adverse Event (AE) is defined as any untoward medical occurrence in a subject undergoing surgery in this trial which does not necessarily have a causal relationship with this intervention. An AE can, therefore, be any unfavorable and unintended sign (including an abnormal laboratory finding), symptom, or disease temporally associated with the use of the one of the devices, whether or not the event is considered causally related to the use of the device. Any worsening of a pre-existing condition or illness is considered an AE. Laboratory abnormalities and changes in vital signs are considered to be AEs only if they result in discontinuation from the study, necessitate therapeutic medical intervention that could impact the study's surgical outcomes, and/or if the Investigator considers them to be AEs.

9.1.2 Serious Adverse Event

Any AE that results in one or more of the following is considered a Serious Adverse Event (SAE): death, life threatening situation, inpatient hospitalization, persistent or significant disability/incapacity, and other medically important events. Definitions of SAEs are:

Death: the subject dies during participation in the study.

Life threatening situation: the subject is at risk of death at the time of the event, but does not refer to the hypothetical risk of death if the AE were more severe or were to progress.

Inpatient hospitalization: a subject requires hospitalization or prolongation of an existing hospitalization, including medical or surgical intervention to prevent permanent impairment to a body structure or body function during participation in a clinical study.

Persistent or significant disability/incapacity: any AE having an outcome that is associated with a substantial disruption of the ability to carry out normal life functions. This includes the inability to work, but is not intended to include transient interruptions of daily activities.

Other medically important events: important medical events that may not result in death, be life-threatening, or require hospitalization (including emergency room visits) but may be considered a serious AE when, based upon medical judgment, they may jeopardize the subject.

Reports of all Serious Adverse Events (SAEs), as classified by the Investigator, will be reviewed on a periodic basis by the Medical Monitor.

9.1.3 Subsequent Surgical Interventions

The cause for subsequent surgical interventions should be listed as a serious adverse event.

Subsequent surgical interventions are classified as follows:

Revision: a procedure that adjusts or in any way modifies the original implant configuration. A revision may also include adjusting the position of the original configuration.

Removal: a procedure where all of the original system configuration are removed with or without replacement.

Supplemental Fixation: a procedure in which additional instrumentation not under study in the protocol is implanted.

Reoperation: any surgical procedure at the involved level that does not require removal, modification, or addition of any components to the system.

9.2 Adverse Event Reporting

Any AE that occurs during the subject's participation in the study will be recorded on the Adverse Event case report form. Pre-existing medical conditions or symptoms occurring prior to the initiation of the study will not be reported as AEs but a worsening of a pre-existing medical condition or symptom will be reported as an AE. Pain, neurological status and functional impairment should be considered AEs when a subject's complaint for any of these symptoms results in an unscheduled visit or when a subject presents with new or worsening symptoms as compared to a previous visit.

All AEs will be followed until the event is resolved or considered to be stable. Relevant source documentation must be available to confirm the occurrence of an AE and must be provided to the sponsor upon request.

9.2.1 Serious Adverse Event Reporting

Independent of the relationship to the study device or procedure, the site must report SAEs to the Sponsor immediately upon becoming aware of the events and subsequently submit the appropriate CRFs within 10 working days. SAEs will be investigated and reported to the FDA if they fall within the appropriate guidelines for Medical Device Reporting (MDR). The site must also report SAEs to the reviewing Institutional Review Board (IRB) according to IRB requirements.

The site must confirm the SAE in appropriate source documents and provide detailed information pertaining to the event to the sponsor and reviewing IRB if requested.

9.3 Adverse Event Severity

The Investigator will be asked to characterize the severity of each AE as mild, moderate or severe. The assessment is subjective and the Investigator will use medical judgment to compare the reported AE to similar types of events observed in clinical practice. Guidelines for AE severity assessment are as follows:

Mild: The AE is transient and easily tolerated by the subject. No medical treatment required.

Moderate: The AE causes the subject discomfort and interrupts the subject's usual activities. Medical treatment required to alleviate or lessen the impact of this untoward condition.

Severe: The AE causes considerable interference with the subject's usual activities may be incapacitating and may require hospitalization. See **Section 9.1.3 Serious Adverse Events**.

9.4 Adverse Event Association

The relationship of all AEs to the device, the procedure or general surgery will be classified by the Investigator as not related, possibly related, probably related or definitely related.

Not related: The AE is due to an underlying or concurrent illness or effect of another device, drug or intervention and is not related to the study device, procedure or general surgery.

Possibly related: The causal and/or temporal relationship to the study device, procedure or general surgery, is equally or less likely than other plausible explanations.

Probably related: The causal and/or temporal relationship to the study device, procedure or general surgery, is likely or significantly more likely than other plausible explanations.

Definitely related: A clinical event that can only be attributed to the device, procedure or general surgery.

9.5 Potential Risks and Anticipated Adverse Events

9.5.1 General Surgery Risks

General surgical risks are but may not be limited to:

- Airway obstruction
- Anaphylaxis

 • Anesthesia related • Atelectasis • Blood clots, including pulmonary emboli • Cardiac arrest • Cardiac, other • CVA • Death • Decompensation • Deep vein thrombosis • Epidural fibrosis • Epidural hematoma or bleeding • Excessive blood loss • Hemorrhage, possibly requiring blood transfusion • Infection, deep wound 	
 • Infection, superficial wound • Infection, urinary tract • Infection, other • Myocardial infarction • Phlebitis • Pleural effusion • Pneumonia • Pneumothorax • Poor tissue healing • Retained sponge • Septicemia • Suture abscess • Transfusion reaction • Vascular or blood vessel injury • Wound dehiscence
---	--

9.5.2 Posterior Fusion Surgery Risks

Posterior Fusion surgical risks are but may not be limited to:

- Allergic reaction to the implant/retractor materials
- Bowel and bladder dysfunction
- Disc height loss
- Dural tear, with or without CSF leak
- Dysesthesia or numbness
- Erosion due to implant
- Failure to relieve symptoms including unresolved pain
- Foreign body reaction
- Kyphosis or hyperextension
- Loss of spine flexibility
- Muscle and tissue injury or damage
- Nerve injury
- Nerve root injury
- Osteolysis
- Pain, new onset
- Pain, unresolved
- Paralysis
- Pseudoarthrosis
- Sexual dysfunction
- Spinal cord damage
- Spinal degradation
- Spinous process fracture
- Surgical intervention at incorrect level
- Thigh pain
- Tingling
- Vertebral body fracture
- Weakness

9.5.3 K2M Device Risks

Risks specific to the VESUVIUS Demineralized Fibers and EVEREST system are but may not be limited to:

- Bone graft migration
- Bone graft subsidence
- Device instability
- Device malposition
- Device migration
- Device subsidence
- Disengagement – from bone
- Disengagement – screw/rod interface
- Foreign body reaction
- Hook/rod interface disengagement
- Material degradation
- Prominent implants
- Rod breakage
- Screw back-out
- Screw breakage
- Screw/rod interface slide
- Set screw loosening

10 SITE REGULATORY REQUIREMENTS

10.1 Institutional Review Board (IRB) Approval

Prior to enrolling subjects in the study, site IRB approval must be obtained according to 21 CFR Part 56. IRB approval must be maintained by the site throughout the study. The IRB approval letter(s) must be maintained in the study files at all times.

10.2 Study Specific Informed Consent

A study specific sample informed consent will be provided to each site prior to the IRB process. The sample informed consent should be used as a template for creating the IRB specific informed consent. Prior to submission of the proposed informed consent to the reviewing IRB, the Sponsor must review the informed consent for completeness according to the protocol and according to 21 CFR Part 50. Potential study subjects should be offered informed consent according to the process outlined in **Section 8.1, Patient Screening and Enrollment**.

Patients must not be offered informed consent until written proof of IRB approval is attained. The patient should be given the opportunity to take home a copy of the informed consent to review and discuss with family members or acquaintances prior to signing. Potential study subjects must also be given the opportunity to discuss the procedure, risks, benefits, alternative treatments and study requirements prior to signing the informed consent. Patients should be informed that they are free to refuse participation in this study and refusal will not affect their medical treatment. If patients elect to participate, it should be made clear that they may withdraw from the study for any reason and at any time without prejudicing further care.

A copy of the signed and dated IRB approved informed consent should be given to all subjects.

10.3 Regulatory Documents

Prior to patient enrollment, the following documents must be provided to the Sponsor and be on file at the site:

- Curriculum vitae and copy of medical license for Principal and Sub-Investigators
- IRB approval letter and IRB roster
- IRB approved Informed Consent Form
- Signed Clinical Research Agreement
- Signed Investigators agreement for Principal and Sub-Investigators, as required
- Finalized budget agreement
- Financial disclosures for the Principal and Sub-Investigators
- Site Initiation documentation

11 SITE VISIT/MONITORING PROCEDURES

Monitoring of the study will be a continuous process conducted in accordance with 21 CFR 812.46 and applicable Sponsor procedures. Monitoring will be performed by qualified clinical research personnel, or designees, of K2M.

11.1 Site Qualification Visit

Prior to selecting an Investigator for participation in the study a Qualification visit will be performed. The purpose of the visit is to confirm that the Investigator/investigative site has adequate staff, including a designated Study Coordinator, and facilities to perform the study according to the requirements of the protocol.

11.2 Study Initiation Visit

Prior to enrolling subjects at a study site, a Site Initiation Visit will be performed. The purpose of the visit is to confirm that the site continues to be qualified for participation and to review the Investigator/site responsibilities and requirements for the study. Site training will be performed and will include:

- Review of the clinical protocol and data collection process
- Monitoring requirements
- IRB requirements
- Informed Consent process
- Review of site records

11.3 Periodic Monitoring Visits

Periodic site monitoring visits will be performed during the study by a designated study monitor assigned by the Sponsor. The purposes of the visits are to confirm compliance to the protocol, review regulatory documents, accurate and complete records are being maintained and to compare source documents to completed CRFs for completeness and consistency. The initial monitoring visit to a site will be scheduled soon after the first 2 to 5 patients are enrolled in the study and may occur prior to the first surgery. The frequency of subsequent visits will be dependent upon the rate of enrollment and site performance on previous monitoring visits. If possible, monitoring visits will be performed at least quarterly. Specific assessments during a monitoring visit include:

- Continued site acceptability
- Compliance to the protocol
- IRB approval status
- Use of the approved informed consent
- Adequacy of source documents
- Complete and accurate CRFs
- Reporting of adverse events
- Protocol deviations
- Site records

If it is determined during a monitoring visit that there are significant non-compliance issues at a site, including adherence to the protocol or applicable regulatory requirements, the issues will be discussed with the Investigator and Study Coordinator and the site will be instructed how to gain compliance. If continued non-compliance is detected on a subsequent monitoring visit, it may be necessary to terminate site participation in the study.

11.4 Final Close-Out Visit

At the completion of the last long-term follow-up visit at each site a final close-out visit will be performed. The purpose of the visit will be to:

- Reconcile all outstanding data queries
- Review site records
- Review the records retention requirements for the study
- Review the final IRB requirements for the study

12 STATISTICAL METHODS

12.1 Study Design

Prospective, single arm, multi-center study with historical controls to evaluate radiographic and clinical outcome variables of the VESUVIUS Demineralized Fibers and the EVEREST Spinal System compared to literature reported outcomes for patients with spinal stenosis, spondylolisthesis, and/or degenerative disc disease treated using traditional autograft with posterior stabilization. Subjects undergoing fusion with the VESUVIUS Demineralized Fibers and the EVEREST Spinal System may also receive an interbody spacer (using the TLIF technique) based on the physician's standard of care.

12.2 Study Hypotheses

The primary study endpoint is the rate of fusion at 24 months. The primary hypothesis of this trial is that the fusion rate with the VESUVIUS Demineralized Fibers and the EVEREST Spinal System combination is non-inferior to the fusion rate achieved and reported with the traditional fusion utilizing autograft and posterior stabilization.

A PubMed literature review was conducted to assemble relevant publications utilizing results from posterior fusion surgeries incorporating osteobiologics. Searches included all peer-reviewed journals published between January 2000 and April 2013. Sample sizes, patient populations, evaluated variables, results, and recorded complications were assessed for each selected article. Only articles describing the use of autograft in comparable patient populations were incorporated into the results. The following table gives the fusion rates found during the literature review:

Papers*	Number of Cases	Number of Fusions	Fusion Rate
Paper 1 ¹	81	44	54.3%
Paper 2A ²	39	34	87.2%
Paper 2B	35	29	82.9%
Paper 3 ³	36	15	41.7%
Paper 4 ⁴	45	33	73.3%
Paper 5A ⁵	21	19	90.5%
Paper 5B	22	20	90.9%
Paper 6A ⁶	10	10	100.0%
Paper 6B	10	10	100.0%
Paper 7A ⁷	47	44	93.6%
Paper 7B	48	42	87.5%
Paper 8A ⁸	42	31	73.8%
Paper 8B	42	24	57.1%
Pooled	478	355	74.3%

* Refer to Appendix 2 for references

A total of 355 successes in 478 subjects gives an overall fusion rate of 74.3%. The hypotheses to be tested for this primary endpoint are as follows:

$$H_0: P_{K2M} \leq P_0 - \delta$$

$$H_A: P_{K2M} > P_0 - \delta$$

where P_{K2M} is the success rate of the VESUVIUS Demineralized Fibers and the EVEREST Spinal System combination, P_0 is the literature success rate of 74.3% and δ is the non-inferiority margin of 10% against the historical success rate.

12.4 Analysis Populations

Analysis Populations are defined as follows:

- The Intent-to-Treat (ITT) population includes all enrolled subjects.
- The Per-Protocol population includes all enrolled subjects who have no major protocol violations (defined as not meeting inclusion/exclusion criteria or not being consented properly).

The fusion analysis will be performed on the ITT population. Analysis of the per-protocol population will be confirmatory of the ITT analysis. The safety analysis will be performed on the ITT population.

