8 STUDY ENROLLMENT/EVALUATIONS

8.1 Patient Screening and Enrollment

Consecutive patients who potentially meet the study inclusion and exclusion criteria will be screened for eligibility. The screening process will be as follows:

- Consecutive patients are potentially eligible for entry into the study based on their age and whether their medical condition appears to generally fit the characteristics specific to this study.
- Patients who agree to enter the study must sign the approved informed consent form.
- A patient is considered enrolled in the study after signing the IRB approved informed consent. Consented patients complete the remainder of the screening process to confirm study eligibility. Patients who do not fulfill the screening criteria are considered Screening Failures and will be documented on the Screening and Enrollment Log. Screening failures will not count against the total number of subjects eligible for analysis.
- Diagnostic imaging studies (standing x-rays) MUST be completed within 180 days of the planned surgery. For diagnostic purposes, an optional pre-op MRI may also be done, per surgeon's standard of care, but does not serve as a substitute for standing x-rays.
- Subject self-assessment questionnaires must be completed within 90 days of the planned date of surgery.
- Subjects who have signed the informed consent and fulfilled the Inclusion/Exclusion criteria are then scheduled for surgery.
- If study surgery is unable to be completed within 90 days of the date of screening, the patient self-assessment questionnaires must be repeated and the site must assess whether any imaging studies need to be repeated (these must be dated within 180 days of surgery). If any imaging study is outside the screening window and has to be repeated, the subject must be exited from the study, re-consented, and assigned a new Subject ID number for re-screening. The Screening Log will provide a means to identify the original Subject ID number for any subjects who are rescreened.

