The TLIF approach with the EVEREST Spinal System also allows for auxiliary procedures for decompression of the spinal cord, correction of spondylolisthesis, correction of disc space collapse or mild kyphosis, as may be medically indicated.

Once the interbody implant is in place and bone graft added to the disc space, distraction is released and compression is applied to the pedicle screw to load the anterior implant and restore lordosis to the spine.

Posterolateral/Transverse Process Fusion and use of VESUVIUS Demineralized Fibers. For each level of the posterolateral fusion, local bone (amount used is to be estimated and recorded) is supplemented with VESUVIUS Demineralized Fibers and bone marrow aspirate (BMA)². The Fibers and BMA are to be combined in a 3:2 volumetric ratio (i.e., a minimum of 15cc Fibers and 10ml BMA are required for a one-level case). If BMA volumes are insufficient to achieve a 3:2 ratio, BMA may be supplemented with venous-line blood. The bone graft, extended with a minimum of 15cc VESUVIUS Fibers and 10ml BMA per level, is then evenly distributed to the right and left lateral gutters. Local bone may be obtained from the levels to be fused, as well as from no more than one additional level of decompression above the target level(s).

The interspinous ligament, if preserved, will serve to prevent graft migration into the exposed portion of the spinal canal and foramen. Care must be taken when placing graft on the ipsilateral intertransverse region to avoid allowing graft to enter the spinal canal or compress the exiting nerve root. Before closure, inspect the neurologic elements to ensure that no graft material has fallen into the spinal canal.

² Obtained from the anterior iliac crest and/or vertebral body (refer to detailed instructions provided in Appendix 1 of this protocol)

Surgical Close and Recovery. Standard procedures and precautions are to be followed for closure of the surgical incision and postoperative recovery. The patient is typically mobilized out of bed the day after surgery; bracing is not required but can be used according to surgeon preference. The subject may be instructed to return to normal activity at the discretion of the Investigator.

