Additional post-operative restrictions may be imposed according to the standard of care normally utilized by the Investigator. In addition, subjects should be instructed to notify the Investigator if experiencing untoward events including but not limited to noticeable pain, numbness, tingling, or weakness that does not decrease with rest, swelling of the lower extremities that does not decrease, or increased pain, erythema, edema or drainage from the surgical incision. The Investigator should then determine if an evaluation is warranted.

A Subject may be withdrawn from the study intra-operatively at the discretion of the Investigator if unexpected findings/occurrences dictate deviation from the intended study procedure. Justification for an intra-operative withdrawal and alternative surgical procedure must be fully documented in the subject's medical record and on the Study Exit case report form.

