8.9 Subject Lost to Follow-Up

Every attempt will be made to have all subjects complete the follow-up visit schedule as specified in the protocol. A subject will not be considered lost to follow-up unless efforts to obtain compliance are unsuccessful. If a subject misses a follow-up visit, the site must document attempts to contact the subject by phone twice. If both contact attempts are unsuccessful, a certified letter from the Investigator must be sent to the subject's last known address indicating the subject's commitment to the study and site contact information to arrange a visit. If the subject does not respond, only then will the subject be considered lost to follow-up. If a subject is lost to follow-up, a Study Exit case report form, including a full description of the attempts to locate the subject, must be completed.

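### The per-protocol set in section 12.4 has no treatment-received condition, so the analysis called confirmatory does not test sensitivity to non-receipt of the study product.

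*Combined protocol and SAP*

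**What the plan says.** Section 12.4 defines two sets. For the first, "The Intent-to-Treat (ITT) population includes all enrolled subjects". The second is the same group restricted to subjects with "no major protocol violations (defined as not meeting inclusion/exclusion criteria or not being consented properly"). The fusion analysis is run on ITT, and "Analysis of the per-protocol population will be confirmatory of the ITT analysis".

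Three other places decide who falls into these sets:

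- Section 8.1 fixes the moment of entry: "A patient is considered enrolled in the study after signing the IRB approved informed consent". It also states that "Screening failures will not count against the total number of subjects eligible for analysis".
- Section 8.3 foresees a change of plan in theatre: "A Subject may be withdrawn from the study intra-operatively at the discretion of the Investigator". The reason and the alternative surgery are documented, and a Study Exit form is completed.
- Section 8.3 sets the graft requirement, with the bone graft "extended with a minimum of 15cc VESUVIUS Fibers and 10ml BMA per level".

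Section 12.2 states the primary hypothesis for the fusion rate with the VESUVIUS and EVEREST combination. Section 12.5 tests that combination's rate against 64.3%.

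**The concern.** A per-protocol analysis offered as confirmation should show whether the conclusion holds among subjects treated as the hypothesis supposes. Here the only grounds for exclusion are failed eligibility and improper consent, and both are settled before the operation. Nothing that happens in theatre can remove a subject from the set. An eligible, properly consented subject whose surgery is cancelled, who is switched to another procedure, or whose graft departs from section 8.3 stays in both sets.

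Agreement between the two analyses would then say little about the product. The two sets handle non-receipt identically, so they agree on that question by construction. A reader of the final report could take that agreement as evidence that the result does not depend on who received the graft, and the analysis would not have examined this.

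**Working it through.** **1. Who is in which set.** Applying sections 8.1, 8.3 and 12.4 as written:

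| Subject | ITT | Per-protocol as written | With a treatment-received condition |
|---|---|---|---|
| Screening failure | no (8.1) | no | no |
| Treated, later found ineligible or improperly consented | yes | no | no |
| Eligible, consented, surgery never done | yes | yes | no |
| Withdrawn intra-operatively to another procedure | yes | yes | no |
| Graft not given as 8.3 describes | yes | yes | no |
| Treated as described | yes | yes | yes |

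The two existing sets differ only in the second row. Rows three to five are the gap.

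**2. How close the two sets are.** With k eligibility or consent violations among 204, the per-protocol set has 204 − k subjects. The documents give no k, so these values are assumptions: k = 0 gives 204 (100%), k = 2 gives 202 (99.0%), k = 5 gives 199 (97.5%) and k = 10 gives 194 (95.1%).

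**3. The plan's own power figure.** The inputs come from sections 12.2, 12.3 and 12.5: one-sided 0.05 exact binomial test, null rate 74.3% − 10% = 64.3%, assumed true rate 74.3%. The critical count r is the smallest value with P(X ≥ r | n, 0.643) ≤ 0.05. Power is P(X ≥ r | n, 0.743). For n = 173, r = 123, the attained level is 0.0354 and power is 85.3%. This agrees with the stated figure of more than 80%.

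**4. What a smaller per-protocol set would cost.** The same formula, with the true rate held at 74.3%:

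| n | r | Attained level | Power |
|---|---|---|---|
| 204 | 143 | 0.0475 | 92.5% |
| 194 | 137 | 0.0376 | 89.4% |
| 184 | 130 | 0.0411 | 88.7% |
| 173 | 123 | 0.0354 | 85.3% |

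The last row corresponds to the plan's 15% drop-out (204 × 0.85 = 173.4). Power stays above 80% throughout.

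**5. A larger effect that does not belong to this wording.** Suppose a fraction m of the 204 is untreated or unread and every such subject is counted as not fused. The expected rate becomes 0.743 × (1 − m):

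- m = 3%: rate 72.1%, power 76.2%
- m = 5%: rate 70.6%, power 59.5%
- m = 10%: rate 66.9%, power 18.3%
- 31 subjects (15%): rate 63.0%, power 2.0%

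These figures need a rule that scores such subjects as failures. Sections 12.4 and 12.5 contain no such rule. With it, the ITT analysis would fall by the same amount, because the same subjects are in ITT.

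**The case against.** Several arguments run the other way.

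- **The set does confirm something.** It tests whether ineligible or improperly consented subjects drive the result. This stands, and it would be too strong to say that the analysis cannot confirm ITT. The gap is confined to non-receipt of the product.
- **A reader might infer that the definition cuts power from 92.5% to 76%, 59.5% or 18.3%.** The documents do not support this. It depends on counting untreated or unread subjects as failures, which the plan does not state and which would hit ITT equally. The 15% drop-out allowance in section 12.3 points towards leaving such subjects out of the denominator: counting 31 of 204 as failures would leave 2.0% power, which does not fit a plan claiming more than 80%.
- **A reader might infer that fusions from another procedure would be credited to the product.** This is unlikely. Section 8.3 has the switched subject withdrawn with a Study Exit form, so a 24-month study film would not normally follow.
- **The usual non-inferiority argument is weaker here.** In a randomized trial, non-adherence can pull two arms together. This is one arm against a fixed 64.3%. If untreated subjects were scored as failures, success would become harder, so no false claim of non-inferiority is shown.
- **Section 4.2 describes the treatment group as patients treated with both products.** That shows the intent, but section 12.4 builds its sets from enrolment and does not refer to it.
- **Few subjects may be affected.** Screening failures are already out, and nothing in the documents suggests a particular rate of cancelled or switched surgery. This stands and limits the weight of the point.
- **A set limited to subjects with an in-window 24-month reading is a completers' set.** It selects on events after treatment and could lose subjects who did badly. This also stands, and it is why the fix does not include that condition by itself.

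**Conclusion.** The point holds in a narrow form. As written, the per-protocol set keeps eligible, consented subjects who did not receive the study product as described, so the confirmatory analysis is blind to non-receipt although the hypothesis is about the product. This follows from the text of sections 8.1, 8.3 and 12.4 and needs no numerical assumption.

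The effect on the estimated fusion rate cannot be sized: it depends on how many such subjects there are and how they are scored, and the documents give neither. The power figures for the remedy assume a true rate of 74.3% among those analysed.

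It is an inexpensive improvement to a supportive analysis. Success is decided on ITT under sections 12.4 and 12.5, and that decision is unchanged. Subjects with no 24-month reading (section 8.9 foresees loss to follow-up: "If a subject is lost to follow-up, a Study Exit case report form" is completed) raise a separate gap that affects both sets, and redefining per-protocol would not close it.

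**What to change.** Amend section 12.4 before analysis so that the per-protocol set holds enrolled subjects who were eligible, were properly consented, and received both VESUVIUS and EVEREST at every treated level as section 8.3 describes. Keep ITT primary.

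No new data are needed. Section 8.3.1 already records the implanted system details, the surgery details and the quantities of Fibers, marrow aspirate and local bone. The quantity check needs one wording settled first: section 8.3 gives the per-level amounts as a minimum, while Appendix 1 gives them as approximate. The sponsor must reconcile these passages before either serves as an analysis criterion.

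Do not make an in-window 24-month reading a condition unless subjects who had subsequent surgery at the index level for non-union are retained as failures. Write a separate rule for missing 24-month readings and apply it to both sets.

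The cost is a change of SAP wording and a slightly smaller set: power of about 89% if 10 subjects leave (n = 194), and about 85% at n = 173.
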